## 6.6.2 Tepotinib

### *Tepotinib: Recommended Dose*

The proposed clinical dose of 500 mg tepotinib once daily was defined by a translational model-based approach that utilized nonclinical PK and Pd data (inhibition of the MET pathway), nonclinical efficacy data (inhibition of tumor growth), and clinical PK and Pd data, and was confirmed by clinical safety and efficacy data.

In the ongoing Phase II single-arm pivotal study (VISION) that aims to investigate tepotinib in advanced (Stage IIIB/IV) NSCLC with *MET*ex14 skipping alterations or *MET* amplification, daily doses of 500 mg tepotinib were administered after breakfast and shown to be efficacious with an acceptable safety profile, confirming the selected clinical dose and regimen, and this is the labeled dose in US and Japan for patients with NSCLC with *MET*ex14 skipping alterations.

The exposure-efficacy analysis for the primary clinical endpoint in VISION, objective response (OR), shows similar OR rates across the exposure range achieved with administration of the clinical dose of 500 mg. This confirms the simulations from the translational PK/Pd model that predicted biologically meaningful target inhibition in a large proportion of the patient population at the clinical dose of 500 mg.

### *Tepotinib: Dose Modification*

Dependent on circumstances, the Investigator could either temporarily interrupt tepotinib treatment, or continue tepotinib treatment at a lower dose level until the AE related to tepotinib recovers to  $\leq$  Grade 2 or to Baseline values.

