## 1.2 Schema

A high-level schedule of visits / assessments is shown in Section 1.3. Number of participants to be screened is described in Section 9.2.

Abbreviations: 2L = 2nd Line; 3L+ = 3rd Line+; DLT = Dose Limiting Toxicity; QD = once daily; RP2D = Recommended Phase II Dose; SMC = Safety Monitoring Committee; US = United States.

- a Required loading dose at an initial dose of 400 mg/m^2 body surface area if participant received the following:
  - Panitumumab as prior line
  - Cetuximab as prior line and last dose was more than 3 weeks ago.No loading dose required if participant received cetuximab as prior line and last dose was given up to 3 weeks ago.
- b The 250 mg once daily dose is the standard dose reduction. If a participant still does not tolerate the 250 mg once daily dose, or the AE does not resolve following treatment interruption, permanent treatment discontinuation or other dosing schemas should be discussed with the Sponsor.
- c Cohort A will include participants from outside the US. A futility analysis is considered which will be performed after 12 participants are enrolled and monitored without stopping recruitment of further participants into this study.
- d After the safety run-in period, at least 16 additional participants will be enrolled at the RP2D expansion in Cohort A, in addition to the 6 participants completing the safety run-in at RP2D.
- e Cohort B will include US participants only.

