### Edema

Edema has been reported frequently in the study program. It is an identified risk for treatment with tepotinib. To gain further information, to the occurrence and resolution of edema, any AEs of edema, the current edema status or AE resolution is to be specifically documented at each visit.

In the case of edema, please follow the advice in the Recommended Dose Modifications for Tepotinib table in Section 6.6.2.

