#### Dose Reduction

In case a dose reduction is necessary, the study intervention will be administered as follows:

The 250 mg once daily dose is the standard dose reduction. If a participant does not tolerate the 250 mg once daily dose, or the AE does not resolve following treatment interruption, permanent treatment discontinuation or other dosing schemas (i.e. holiday schedules or tepotinib every 2nd day) should be discussed with the Sponsor.

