**Recommended Dose Modifications for Tepotinib**

Target organ	Adverse event a	Dose modification
Pulmonary	Confirmed ILD/pneumonitis	Permanently discontinue tepotinib.
Cardiac	QTc interval prolongation of Grade $\geq 3$	Discontinue tepotinib
Body	Edema Grade 1 or 2	Dose level of tepotinib can be maintained
	Edema Grade 3	
The dose of tepotinib must be interrupted until edema recovers to <math>\leq</math> Grade 2 or baseline but for no more than 21 days.
 
After recovery the patient can restart at the same dose or at 250 mg daily.
 
If edema Grade 3 reoccurs the tepotinib dose must be interrupted again until edema recovers to <math>\leq</math> Grade 2 or baseline but for no more than 21 days. After recovery, tepotinib must then be dose reduced to 250 mg daily (if the previous dose was 500 mg daily).
 
If edema Grade 3 reoccurs at 250 mg dose, tepotinib must be permanently discontinued.

	Generalised edema Grade 4	Permanently discontinue tepotinib.
	Pancreatic enzyme elevation Grade $\geq 3$	See detailed instruction in Section 6.5.4.2.
Other	Any other related adverse event of Grade 3	
The dose of tepotinib must be interrupted until event resolves to <math>\leq</math> Grade 2 or baseline but for no more than 21 days. After recovery, tepotinib may be restarted at 1 dose level below; 250 mg daily.
 
If any other related AE of Grade 3 reoccurs at 250 mg dose, tepotinib must be permanently discontinued

	Grade 4	Permanently discontinue tepotinib

Abbreviation: AE = adverse event; .

Also consider DLT rules during DLT period and Safety Run-in.

a Adverse events graded by NCI-CTCAE v5.0.

Following dose modifications, the dose of tepotinib may be increased again to the initial dose level at the discretion of the Investigator.

Clinical circumstances which are not covered by above criteria may be grounds for dose reductions or treatment interruptions and should be discussed with the Sponsor on a case-by-case basis.

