- for the first cycle:
 - $400 \text{ mg/m}^2 + 2 \times 250 \text{ mg/m}^2$ per 3-week cycle, if loading dose is needed
 - $3 \times 250 \text{ mg/m}^2$ per 3-week cycle, if loading dose is not needed
- for the subsequent cycles: $3 \times 250 \text{ mg/m}^2$ per 3-week cycle

Dose reductions

If the 500 mg dose for tepotinib will be the selected RP2D, participants may have a dose reduction to 250 mg, which is also the minimum possible dose in this study. If 250 mg is the RP2D for tepotinib, then no further reduction will be possible.

For cetuximab the loading dose is 400 mg/m² and subsequent weekly doses are 250 mg/m² if the loading dose is required or the weekly dose is 250 mg/m² if the loading dose is not required. The weekly dose can be reduced to 200 mg/m² or 150 mg/m² for safety reasons if necessary.

The number of participants with and without any dose reduction will be summarized. In case the selected RP2D is 250 mg, the tepotinib sections will contain “NA” (Not Applicable).

Number of participants with any dose adjustment due to Adverse Event/Other will be provided.

Dose interruptions and therapy delays

For tepotinib any days within the treatment period where the participants did not take any tepotinib will be counted as dose interruptions. Number of participants with any tepotinib interruptions will be presented.

Dose delays are applicable for cetuximab only. It will be derived by administration as the number of days between two successive administrations greater than 7 and will be presented as follows:

- Number of participants with delayed infusions, and maximum length of delay (no delay, 3-8 days, 9-15 days, ≥ 16 days) – worst case

Treatment administration of tepotinib and cetuximab by time point will be listed.

14 Efficacy Analyses

The following analyses will be performed based on the FAS and will be presented by cohort and assigned dose level of tepotinib, except when otherwise stated.

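### Protocol 6.6.2 lets tepotinib continue at a lower dose through related Grade 3 or 4 events that its own table says must be interrupted or permanently stopped

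*Protocol*

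**What the plan says.** The general sentence under Tepotinib: Dose Modification (Protocol 6.6.2) reads: "Dependent on circumstances, the Investigator could either temporarily interrupt tepotinib treatment, or continue tepotinib treatment at a lower dose level". The choice lasts until the related event has come down to Grade 2 or lower or to baseline.

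The table of recommended modifications follows. For related Grade 3 events not listed in another row it says: "The dose of tepotinib must be interrupted until event resolves to" Grade 2 or lower or baseline, for at most 21 days. The 250 mg dose appears only as a restart dose after recovery. The row then adds: "If any other related AE of Grade 3 reoccurs at 250 mg dose, tepotinib must be permanently discontinued". The next row makes Grade 4 a permanent stop.

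The line closing the section keeps individual discussion with the Sponsor for what the table leaves out: "Clinical circumstances which are not covered by above criteria may be grounds for dose reductions or treatment interruptions".

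For edema, Protocol 6.5.4.2 says which text to use: "In the case of edema, please follow the advice in the Recommended Dose Modifications for Tepotinib table in Section 6.6.2".

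On intolerance at 250 mg, the Dose Reduction paragraph of 6.6.2 offers "permanent treatment discontinuation or other dosing schemas" for discussion with the Sponsor. Footnote b of the schema (Protocol 1.2) does the same, beginning "If a participant still does not tolerate the 250 mg once daily dose".

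**The concern.** For the same related toxicity, one part of 6.6.2 allows dosing to go on at a reduced level and another part requires it to stop. Both are stated rules, so this is a conflict and not a missing detail. An Investigator who acts on the general sentence as written would give tepotinib during a Grade 3 event that the table says must be interrupted, or during a Grade 4 event that the table says ends treatment. What is at stake is the participant's exposure during a severe related toxicity, and whether sites handle the same event in the same way.

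**Working it through.** No arithmetic applies beyond a count of table entries. The check compares the texts.

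**Step 1: which grades the general sentence reaches.** Its end point is recovery to Grade 2 or lower, or baseline. An event that still has to recover to Grade 2 is at Grade 3 or above. The sentence names no maximum, so Grade 4 falls within it.

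**Step 2: which table entries are settled elsewhere.**

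| Table entry | Action in the table | Settled by | Does the general sentence still compete? |
|---|---|---|---|
| Confirmed ILD/pneumonitis | Permanent stop | Same rule in 6.5.4.2 | No |
| QTc prolongation, Grade 3 or higher | Stop | Same rule in 7.1 | No |
| Edema, Grade 1 or 2 | Dose may stay | 6.5.4.2 points to the table | No |
| Edema, Grade 3 | Interrupt, up to 21 days | 6.5.4.2 points to the table | No |
| Generalised edema, Grade 4 | Permanent stop | 6.5.4.2 points to the table | No |
| Pancreatic enzymes, Grade 3 or higher | Refers to 6.5.4.2 | Detailed rules in 6.5.4.2 | No |
| Other related events, Grade 3 | Interrupt, up to 21 days; 250 mg only after recovery | Nothing found | Yes |
| Grade 4 (under the same Other heading) | Permanent stop | Nothing found | Yes |

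Of eight entries, six are settled, so 8 − 6 = 2 are left. I read the Grade 4 row as carrying over the limit to related events from the row above it.

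**Step 3: whether anything nearby ranks the two texts.** The footnote on DLT rules tells sites to consider those rules during the run-in, but it does not rank the table against the general sentence. Section 7.1 only asks the Investigator to consider stopping for abnormal liver function, so it does not settle a Grade 3 or 4 transaminase rise. The closing line points towards the table, but by implication only.

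**Step 4: what lands in the two open rows.** Protocol 2.3 lists the adverse reactions to tepotinib. Taking out ILD, edema and amylase/lipase leaves creatinine increase, hypoalbuminemia, AST/ALT increase, diarrhea, and nausea and vomiting. Diarrhea and AST/ALT increase are also among the overlapping toxicities named there for this combination. The same section describes those two as generally mild to moderate, so the open rows concern their severe end.

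**Step 5: recurrence at 250 mg.** The Dose Reduction paragraph and footnote b cover any intolerance at 250 mg and list permanent discontinuation as one option. The table fixes that option for one subset, a recurrent related Grade 3 event. Stopping under the table is consistent with both texts, so this is a general rule narrowed by a specific one. A cross-reference is missing, which is a minor matter.

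**Step 6: dependence on the RP2D.** SAP Section 13 (Dose reductions) says: "If 250 mg is the RP2D for tepotinib, then no further reduction will be possible". On that account the lower-dose option has nothing to apply to if the RP2D is 250 mg. The conflict therefore matters if the RP2D is 500 mg.

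**The case against.** The best defence is that a specific rule displaces a general one. The opening sentence is permissive and conditional and names no event. The table sets out events by organ and grade, and its catch-all row is mandatory. The closing line keeps discretion for what the table does not cover, which implies that the table decides what it does cover. The summary of changes for Protocol Version 2.0 also describes the table as a safety measure giving guidance by severity grade.

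This stands as evidence of what was intended. It does not remove the permission, which remains in the text without exception, and the table's own title calls its contents recommended. Sites should not have to infer which rule binds for a severe related toxicity.

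Other safeguards limit the consequence. In the run-in, most non-hematological events of Grade 3 or higher are DLTs (6.6.3). Unacceptable toxicity requires withdrawal from treatment (7.1). Immediate safety concerns go to the Sponsor (Section 8), and the SMC reviews safety throughout (9.4.4). These reduce the practical effect but leave the wording conflict in place.

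A reader might go further than the documents allow in four ways:
- **That edema alone has a stated rule.** It does not. Pancreatic enzymes are routed to 6.5.4.2, and ILD and QTc prolongation have their own mandatory rules that agree with the table.
- **That the 250 mg recurrence rule is a second full contradiction.** Step 5 shows that it is not.
- **That protocol-deviation classification is undermined.** SAP 10.2.1 leaves definitions and categories to a study-specific list that is not among the documents and may settle the matter.
- **That the harm can be measured as lost or retained dose intensity.** Any such figure would come from assumed event durations, would not measure risk to participants, and would feed no planned decision.

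**Conclusion.** The concern holds as a conflict in wording that bears on patient safety. It reaches two of the table's eight entries: related events of Grade 3 and of Grade 4 that are not edema, ILD, QTc prolongation or pancreatic enzyme elevation. The intended reading is probably that the table governs, but 6.6.2 does not say so for these rows.

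No frequency can be attached. Protocol 2.3 reports related events of Grade 3 or higher in 51.6% of participants given tepotinib with gefitinib. That is a different partner drug and tumor, and the figure includes events outside these two rows, so it is not an estimate for this study.

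No effect on any endpoint is claimed. The conclusion assumes that the Grade 4 row means related events and that the RP2D is 500 mg. I am confident of the textual mismatch, less so of how often it would change what a site does.

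**What to change.** In Protocol 6.6.2:
- State that the table governs every event it lists, as 6.5.4.2 already does for edema.
- Limit the lower-dose option in the opening sentence to circumstances the table does not cover, in line with the closing line of the section.

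As a minor addition, note in the Dose Reduction paragraph and in schema footnote b (Protocol 1.2) that a related Grade 3 event recurring at 250 mg means permanent discontinuation.

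The cost is a small text change that can go into the next amendment. Protocol Appendix 2 requires IRB/IEC approval before it takes effect. The SAP needs no change.

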#### Dose Reduction

In case a dose reduction is necessary, the study intervention will be administered as follows:

The 250 mg once daily dose is the standard dose reduction. If a participant does not tolerate the 250 mg once daily dose, or the AE does not resolve following treatment interruption, permanent treatment discontinuation or other dosing schemas (i.e. holiday schedules or tepotinib every 2nd day) should be discussed with the Sponsor.

#### Treatment Interruption

The maximum permitted period of continuous treatment interruption is 21 days. Following a treatment interruption, participants can be re-challenged at the initial dose level. Re-exposure at different dose level after a treatment interruption is subject to case by case decisions; the Sponsor should be informed of any such decisions.

**Recommended Dose Modifications for Tepotinib**

Target organ	Adverse event a	Dose modification
Pulmonary	Confirmed ILD/pneumonitis	Permanently discontinue tepotinib.
Cardiac	QTc interval prolongation of Grade $\geq 3$	Discontinue tepotinib
Body	Edema Grade 1 or 2	Dose level of tepotinib can be maintained
	Edema Grade 3	
The dose of tepotinib must be interrupted until edema recovers to <math>\leq</math> Grade 2 or baseline but for no more than 21 days.
 
After recovery the patient can restart at the same dose or at 250 mg daily.
 
If edema Grade 3 reoccurs the tepotinib dose must be interrupted again until edema recovers to <math>\leq</math> Grade 2 or baseline but for no more than 21 days. After recovery, tepotinib must then be dose reduced to 250 mg daily (if the previous dose was 500 mg daily).
 
If edema Grade 3 reoccurs at 250 mg dose, tepotinib must be permanently discontinued.

	Generalised edema Grade 4	Permanently discontinue tepotinib.
	Pancreatic enzyme elevation Grade $\geq 3$	See detailed instruction in Section 6.5.4.2.
Other	Any other related adverse event of Grade 3	
The dose of tepotinib must be interrupted until event resolves to <math>\leq</math> Grade 2 or baseline but for no more than 21 days. After recovery, tepotinib may be restarted at 1 dose level below; 250 mg daily.
 
If any other related AE of Grade 3 reoccurs at 250 mg dose, tepotinib must be permanently discontinued

	Grade 4	Permanently discontinue tepotinib

Abbreviation: AE = adverse event; .

Also consider DLT rules during DLT period and Safety Run-in.

a Adverse events graded by NCI-CTCAE v5.0.

Following dose modifications, the dose of tepotinib may be increased again to the initial dose level at the discretion of the Investigator.

Clinical circumstances which are not covered by above criteria may be grounds for dose reductions or treatment interruptions and should be discussed with the Sponsor on a case-by-case basis.

### 6.6.3 Dose Limiting Toxicity

Dose-limiting toxicities will be evaluated using the NCI-CTCAE v5.0. Limits for dose escalations will be considered in accordance to Bayesian Optimal Interval design (BOIN) based on a maximum target toxicity rate of 30% and a maximum number of 12 participants (Yuan 2016).

In the safety run-in part of the study, DLTs are defined as any of the following toxicities and judged by the Investigator and/or the Sponsor to be not attributable to the disease or disease-related processes under investigation:

1. Grade 4 neutropenia for more than 7 days
2. Grade  $\geq 3$  febrile neutropenia with absolute neutrophil count  $< 1000/\text{mm}^3$  and a single temperature of  $> 38.3^\circ\text{C}$  ( $101^\circ\text{F}$ ) or a sustained temperature of  $\geq 38^\circ\text{C}$  ( $100.4^\circ\text{F}$ ) for more than 1 hour
3. Grade 4 thrombocytopenia or Grade 3 thrombocytopenia with non-traumatic bleeding
4. Grade 3 uncontrolled nausea/vomiting and/or diarrhea that has not improved within 72 hours despite adequate and optimal treatment
5. Grade 4 vomiting and/or diarrhea
6. Grade  $\geq 3$  skin toxicity that has not resolved to Grade 2 after 14 days of adequate treatment
7. Any other Grade  $\geq 3$  non-hematological AE will be defined as DLT. Exceptions are alopecia or an isolated lipase and/or amylase elevation of Grade  $\geq 3$  without clinical or radiological evidence of pancreatitis
8. Occurrence of Hy's law cases (defined as aminotransferases  $> 3 \times \text{ULN}$ , total bilirubin  $\geq 2 \times \text{ULN}$ , and alkaline phosphatase (ALP)  $< 2 \times \text{ULN}$ , with no other reason to account for these abnormalities)
9. Interstitial lung disease (ILD)/pneumonitis.

All participants enrolled in the safety run-in period who miss  $> 25\%$  of the planned doses of tepotinib and/or cetuximab within Cycle 1 will be replaced if the dose reduction/interruption was not caused by any safety reasons/DTLs. Participants who experience at least one DLT during the DLT assessment period are included regardless of the cumulative dose administered.

All participants enrolled in the study are selected based on the same inclusion and exclusion criteria as specified in the eligibility criteria.

## 6.7 Study Intervention after the End of the Study

If the study is prematurely terminated or suspended, participants who continue to demonstrate clinical benefit will be eligible to receive study intervention. Study intervention will be provided via an extension of the study, a rollover study requiring approval by the responsible health authority and independent ethics committee, or mechanisms i.e., single patient post study access, or patient support, or other access programs as per local regulations, at the discretion of the Sponsor. The Sponsor reserves the right to terminate access to study intervention if any of the following occur: a) the study is terminated due to safety concerns, or b) a marketing authorization is granted in the local market and the corresponding medication is reimbursed by the public social security system making it accessible to the participant.

## 7

**Discontinuation of Study Intervention and Participant Discontinuation/Withdrawal**

## 7.1

**Discontinuation of Study Intervention**

In rare instances, it may be necessary for a participant to permanently discontinue (definitive discontinuation) study intervention. If study intervention is definitively discontinued, the participant will remain in the study to be evaluated for what is specified in the Schedule of Activities (SoA) (Section 1.3). The SoA indicates data to be collected at the time of discontinuation of study intervention and follow-up and for any further evaluations that need to be completed.

- The participant must be withdrawn from study intervention in the event of any of the following:
  - Withdrawal of consent.
  - Development of unacceptable toxicity.
  - Occurrence of progressive disease according to RECIST Version 1.1 or initiation of any other anticancer therapy.
  - Occurrence of an inclusion or exclusion criterion that is clinically relevant and affects the participant's safety, if discontinuation is considered necessary by the Investigator and / or Sponsor prior to study intervention completion.
  - Occurrence of pregnancy, which at the EoT visit is done as a serum test only for confirmation as urine test will be positive, before being discharged from the study.
  - Use of a nonpermitted concomitant drug (including any other drug with known anticancer activity unless specified otherwise), if discontinuation is considered necessary by the Investigator and/or the Sponsor.
  - Noncompliance that is deemed by the Investigator or the Sponsor to compromise participant safety or study integrity.

The Investigator will consider discontinuation of study intervention for abnormal liver function when a participant meets one of the conditions outlined and not meeting inclusion criterion 10 under Section 5.1 or if the Investigator believes that it is in best interest of the participant.

The Investigator must consider discontinuation of study intervention for an ILD-like event when a participant meets one of the conditions outlined in Section 6.5.4.1 and Section 6.5.4.2 under Respiratory Disorders and ILD, or if the Investigator believes that it is in best interest of the participant.

If a clinically significant finding is identified (including changes from Baseline in QT interval corrected using Fridericia's formula [QTcF]) after enrollment, the Investigator or qualified designee will determine if the participant can continue in the study and if any change in participant management is needed. If the participant has a Grade  $\geq 3$  QTc interval prolongation study intervention must be discontinued. Additionally, close and appropriate ECG monitoring in hospital

according to local standard should be initiated. This review of the ECG printed at the time of collection will be documented. Any new clinically relevant finding is reported as an AE.

The SoA (Section 1.3) specifies the data to collect at study intervention discontinuation and follow-up, and any additional evaluations that need to be completed. Withdrawals will be documented in the eCRF as per the SoA (Section 1.3).

